### **Caffeinated chewing gum and Placebo**

In this study, the CAF group used two mint-flavored gums containing 100 mg of caffeine each (Military Energy Gum, Arctic Mint Flavor, Stay Alert, Chicago, USA), and the PLA group used two mint-flavored gums of similar appearance and taste without caffeine (Xylitol, Fresh Mint, Lotte Vietnam CO., LTD). Fresh Mint, Lotte Vietnam CO., LTD). The caffeine gum used in this study has been shown to have good absorption and bioavailability (18) and to be effective in improving repetitive sprint performance (19, 20), vertical jump height (20, 21), and upper and lower extremity strength (21). Therefore, the caffeinated chewing gum used in this study was the

product with the supplemental effect. After the participants spit out the gum, verbal questioning was used to confirm whether the participants could differentiate between caffeine gum and placebo. 4 of 14 (29%) fielders and 4 of 10 (40%) pitchers correctly determined the type of gum intervention.

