## **Materials and methods**

### **Experimental design**

This study utilized a randomized, crossover, single-blind experimental design. At least two familiarization tests were conducted one week before the formal trial to ensure

each participant was familiar with the experimental procedures. Before the first formal trial, participants were randomly assigned to either the caffeinated chewing gum trial (CAF) with 200 mg of caffeine or the placebo trial (PLA) without caffeine, seven days apart (Figure 1). The primary outcome was the pitching and hitting performance, and the secondary outcomes were hand grip strength and height of countermovement jump.

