### **Experimental protocol**

All participants are required to take a familiarization test at least two times before the official experiment to ensure that they are familiar with the experimental protocol. The formal trial includes grip strength, vertical jump, pitching, and batting tests. Before the first trial, the participants' diets for the previous two days were recorded, and the participants were asked to consume the same food before the next test, especially breakfast and lunch on the day of the trial. On the day of the experiment, participants were asked to fast for at least 3 hours and arrive at the lab at 3:30 p.m. All experiments were conducted at the same time each week.

When participants arrived at the laboratory, the first formal experiment collected basic information, including age, height, weight, and habitual caffeine intake. Then,

they were randomly assigned to either the CAF or PLA trials. During the formal experiment, a 5-minute break was taken upon arrival at the laboratory, followed by administering caffeinated chewing gum containing 200 mg of caffeine or the placebo gum without caffeine, which was chewed for 10 min and then spit out. 15-min standardized dynamic warm-up exercises were performed after the gum spat out, and the warm-up was conducted the same manner as during the daily training. Grip strength, vertical jump, and softball specialized tests were measured after the warm-up. After the first test, a second test was conducted at the same time one week apart, and the groups were switched to follow the same experimental protocol.

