## **Outcome Measure**

### **Grip Strength**

In the grip strength test, the participant stood in a standing position with a customary hand-held grip dynamometer (Smedley's Hand Grip Dynamometer TTM, Japan) and adjusted the grip to the second knuckle, with the arm at about 10-15 degrees to the trunk, and pressed the grip continuously for about 3 seconds with maximum strength, keeping the trunk stable during the process, performing the procedure three times, with one minute's rest in the middle of each time, and calculating the data averages (22).

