### **Countermovement Jump**

The vertical jump test collected data using a Gymaware (Gymaware, KineticPerformance, Australia) device. The participant wore a belt and attached a lanyard to the belt. During the jumping process, the participant jumped upward as far

as possible after squatting with arms folded at the waist, without interruption of movement, and without flexion of the hip and knee joints when leaving the ground. The jumps were performed three times in total, with a one-minute rest in the middle of each jump, and the data average was calculated (23).

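### Does the count of players who identified their gum (4 of 14 fielders, 4 of 10 pitchers) need changing because it cannot show that they were blind?

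*Protocol*

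**What the plan says.** The Protocol's Experimental design section states: "This study utilized a randomized, crossover, single-blind experimental design". Each player has one caffeine and one placebo session. After the first session a second follows a week later, and "the groups were switched to follow the same experimental protocol".

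The section Caffeinated chewing gum and Placebo describes the blinding check: "After the participants spit out the gum, verbal questioning was used to confirm whether the participants could differentiate between caffeine gum and placebo". The result is one sentence: "4 of 14 (29%) fielders and 4 of 10 (40%) pitchers correctly determined the type of gum intervention". The Protocol adds no benchmark and no interpretation.

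On sequence, the Experimental protocol section says "15-min standardized dynamic warm-up exercises were performed after the gum spat out", and then "Grip strength, vertical jump, and softball specialized tests were measured after the warm-up".

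The Statistical analysis section lists paired t-tests on the performance outcomes. The identification count has no part in them.

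**The concern.** This count is the only evidence in the Protocol that players were blind, and four facts needed to read it are missing.

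- **Session.** The denominators count 24 players, but there were 24 × 2 = 48 gum sessions. In the second session a player can compare with the first.
- **Scoring.** A correct answer could mean right in one session or right in both.
- **Answers.** The 16 players not counted as correct may have named the wrong gum or may have been undecided.
- **Position relative to the tests.** The question came after the gum was spat out, but the text does not say whether it came before or after the warm-up and tests.

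A reader who compares 29% and 40% with 50% will be reassured. That comparison is valid only for a forced choice between two gums, scored once. The placebo is a different commercial product described only as similar, and the primary outcomes are pitching and hitting performance, which expectation could plausibly affect. If the count in fact pointed to unblinding, the single-blind label would be in doubt.

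**Working it through.** **Inputs.** From Caffeinated chewing gum and Placebo: 4 correct of 14 fielders and 4 correct of 10 pitchers. Pooled by addition: 8 of 24, leaving 16 not correct. The chance rates and the numbers undecided below are assumptions, because the Protocol gives none.

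**1. Reproduce the stated figures.** 4/14 = 28.6% and 4/10 = 40.0%, which agree with the printed 29% and 40%. Pooled, 8/24 = 33.3%. Exact (Clopper-Pearson) 95% intervals are 8.4% to 58.1% for fielders, 12.2% to 73.8% for pitchers and 15.6% to 55.3% pooled.

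**2. Compare with fixed chance rates** (two-sided exact binomial test).

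| Assumed rule | Chance | Expected of 24 | Pooled p (8/24) | Fielders p | Pitchers p |
|---|---|---|---|---|---|
| One forced two-way guess | 1/2 | 12 | 0.15 | 0.18 | 0.75 |
| Three equally likely options | 1/3 | 8 | 1.00 | 1.00 | 0.74 |
| Right in both sessions, independent guesses | 1/4 | 6 | 0.35 | 0.76 | 0.28 |

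The pooled result lies 16.7 points below chance, exactly at it, or 8.3 points above it. None of the comparisons is significant.

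The 1/4 row is doubtful. The Participants section says that the complete procedure was explained at recruitment, so players probably knew they would get each gum once. A player who then answers consistently is right in both sessions or in neither, and chance returns to 1/2.

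**3. Vary the number undecided.** A Bang-type index is (correct − wrong)/n, with SE = √{[(correct + wrong)/n − index²]/n}. It is usually calculated per treatment arm. Here it is pooled over the gums because no split is given. The sign test compares correct with wrong answers. With n = 24 and 8 correct:

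| Wrong | Undecided | Index (95% CI) | Sign test p |
|---|---|---|---|
| 16 | 0 | (8 − 16)/24 = −0.33 (−0.71 to 0.04) | 0.15 |
| 8 | 8 | 0 | 1.00 |
| 7 | 9 | (8 − 7)/24 = +0.04 | 1.00 |
| 2 | 14 | +0.25 (0.01 to 0.49) | 0.109 |
| 1 | 15 | +0.29 (0.08 to 0.51) | 0.039 |
| 0 | 16 | +0.33 (0.14 to 0.52) | 2 × (1/2)⁸ = 0.008 |

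By group, the index runs from (4 − 10)/14 = −0.43 to 4/14 = +0.29 for fielders, and from (4 − 6)/10 = −0.20 to 4/10 = +0.40 for pitchers.

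A bare majority undecided (9 of 16) gives an index of +0.04, which shows nothing. The sign test falls below 0.05 only with 15 or 16 of the 16 undecided. The interval for the index just excludes zero at 14.

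**4. Which missing facts move the sign.** Answer options and scoring do. The choice of a single session does not, because a forced two-way guess has chance 1/2 in either week. Timing does not change the chance rate either. It affects only whether a guess reflects the taste of the gum or a felt effect. Timing is also partly given: the question follows spit-out, and asking it then, before the warm-up, is the natural though not certain reading.

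**The case for a change.** The strongest case for acting is that the Protocol itself prints this result and gives its purpose as finding out whether players could tell the gums apart. As printed, the count cannot answer that. At the two ends of the assumed range, the same number gives an index of −0.33 with p=0.15 or +0.33 with p=0.008. A statistical analysis plan would not normally explain how a verbal question was asked. Stating the session, the answers and the scoring would take a few sentences and perhaps a small table from answers already collected.

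Much of this stands. The facts are missing, and 8/24 should not be cited as proof of blinding. What does not follow is that the plan contains an error. The counts and percentages are correct, and the Protocol makes no claim from them. Having 24 results from 48 sessions is not a contradiction, since whether a player can tell the two gums apart can be a single judgement per player. The p=0.008 belongs to the extreme end of an assumed range. Adding a further question after the softball tests would be a debatable preference, since later guesses may reflect perceived performance.

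**Conclusion.** No change to the plan is called for. The count alone neither establishes nor refutes participant blinding: pooled 8/24 = 33% (16% to 55%), with an index anywhere from −0.33 to +0.33 depending on how many of the 16 others were undecided. It is compatible with guessing at each fixed chance rate tried, although intervals this wide do not exclude partial unblinding. It would suggest unblinding only if nearly all of the 16 had been undecided, which nothing in the Protocol indicates.

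The gap is one of description. No stated number or rule is wrong, and filling the gap would leave every paired t-test on the outcomes unchanged. An author reporting the trial would naturally state how the question was put and scored or, if the answers were not kept in that detail, refrain from a conclusion on blinding. The benchmarks and the index range rest on assumed answer options and scoring, and on pooling over the gums. The effect of any unblinding on pitching or hitting cannot be derived from the Protocol.

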## **Outcome Measure**

### **Grip Strength**

In the grip strength test, the participant stood in a standing position with a customary hand-held grip dynamometer (Smedley's Hand Grip Dynamometer TTM, Japan) and adjusted the grip to the second knuckle, with the arm at about 10-15 degrees to the trunk, and pressed the grip continuously for about 3 seconds with maximum strength, keeping the trunk stable during the process, performing the procedure three times, with one minute's rest in the middle of each time, and calculating the data averages (22).

### **Countermovement Jump**

The vertical jump test collected data using a Gymaware (Gymaware, KineticPerformance, Australia) device. The participant wore a belt and attached a lanyard to the belt. During the jumping process, the participant jumped upward as far

as possible after squatting with arms folded at the waist, without interruption of movement, and without flexion of the hip and knee joints when leaving the ground. The jumps were performed three times in total, with a one-minute rest in the middle of each jump, and the data average was calculated (23).

### **Pitching Performance**

The windmill pitching method was used in the pitching performance test. Using the adult women's fastpitch rules, the pitching plate is placed 13.11 meters from the home plate. A green screen is placed behind the home plate, and the location of the tape is marked. The player is asked to throw each ball to the target location. Each set consisted of 10 fastballs, three sets in total. Pitching data were collected and analyzed using Rapsodo Pitching 2.0 (Rapsodo Baseball System, Rapsodo Inc, Fisher, IN). This device has been used in the literature and has been found to have high reliability for both hitting and pitching measurements (24, 25). During the test, the device was placed 15.6 feet from the front edge of the home plate according to the manual to ensure data accuracy. The pitching test evaluates average and maximum fastball velocity and average fastball spin rate.

### **Hitting Performance**

Hit off Tee was used in the hitting performance test. The T-base is placed on the front edge of the center of the home plate, adjusted to the height of the participant's navel, and set up the stance consistently. A target is set 10 meters in front of the home plate at a height angle of 10 degrees, requiring the participant to hit each ball to the target position. There were five sets of 5 swings per set. Hitting data were collected and analyzed using Rapsodo Hitting 2.0 (Rapsodo Baseball System, Rapsodo Inc, Fisher, IN). During the test, the device was placed 14 feet from the front edge of the home plate according to the instruction manual to ensure data accuracy. The batting test evaluates average exit speed and maximum exit speed.

### **Statistical analysis**

Data from this study were presented as mean  $\pm$  standard deviation and analyzed using SPSS 23.0 statistical software. The Shapiro–Wilk test was conducted to test the normality of the data. Paired samples t-tests were used to compare hand grip strength, countermovement jump, average exit speed, max exit speed, average fastball speed, max fastball speed, and average fastball spin rate. The significance level was set at  $\alpha < 0.05$ .

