# **Effects of caffeinated gum on a Batting and Pitching Performance of Female Softball Players: a crossover trial**

**Document Date: May 22, 2022**

## **Project summary**

The purpose of this study was to investigate the effects of caffeinated chewing gum on female softball pitching and hitting performance. 24 trained female softball players (10 pitchers and 14 fielders) were divided into a caffeine chewing gum trial (CAF) or a placebo trial (PLA) in a single-blind, randomized, crossover experimental design. Two pieces of gum containing 100 mg of caffeine (CAF) or without caffeine (PLA) were chewed for 10 minutes and then spit out, followed by a 15-minute warm-up. The physical tests included grip strength and countermovement jump. The softball-specific tests included pitching (fast ball speed) or hitting (exit speed). The two trials were separated by seven days.

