## **Participants**

Twenty-four trained female softball players without the habit of caffeine intake were recruited in this study as participants. The participants included fourteen fielders (age  $20.3 \pm 1.3$  years; height  $159.5 \pm 5.2$  cm; body mass  $58.1 \pm 6.9$  kg; habitual caffeine intake  $37.4 \pm 10.2$  mg/day) and ten pitchers (age  $20.5 \pm 1.3$  years; height  $163.9 \pm 4.6$  cm; body mass  $68.0 \pm 6.7$  kg; habitual caffeine intake:  $26.3 \pm 6.5$  mg/day). Inclusion criteria are 1. adult female; 2. at least six years of professional softball training and familiarity with all softball skills; 3. caffeine intake of less than 80 mg daily. Exclusion criteria were: 1. not professionally trained; 2. having a medical condition for which exercise is not recommended, such as hypertension, hyperlipidemia, or heart disease; 3. having any musculoskeletal injuries within the last six months or not being able to complete a full trial; 4. having a history of caffeine allergy.

Participants were asked to avoid excessive training or vigorous exercise for 72

hours before each formal trial and avoid caffeine or alcohol for 24 hours before each test. At the time of recruitment, the purpose of the experiment, the complete procedure, and the potential risks were explained. Participants will read and sign the consent form to ensure they understand the entire process and their rights before the experiment. This study was approved by the Institutional Review Board of Jen-Ai Hospital - Dali Branch (111-22). This study follows the principles of the Declaration of Helsinki and the recommendations proposed by the CONSORT Statement.

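### The paired t-tests carry no period term, so any week-to-week shift biases the caffeine estimate when the sequences are unequal and costs power when they are equal

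*Protocol*

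**What the plan says.** The Protocol describes the design under Experimental design: "This study utilized a randomized, crossover, single-blind experimental design". Allocation is by chance: "participants were randomly assigned to either the caffeinated chewing gum trial (CAF) with 200 mg of caffeine or the placebo trial (PLA". The Experimental protocol section adds the second period: "After the first test, a second test was conducted at the same time one week apart, and the groups were switched". No ratio, block, stratum or number per sequence is given.

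The primary outcome is pitching and hitting performance. Each is measured in one kind of player, as the Project summary says: "The softball-specific tests included pitching (fast ball speed) or hitting (exit speed". The primary comparisons therefore rest on 10 pitchers and 14 fielders.

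The Statistical analysis section names the test: "Paired samples t-tests were used to compare hand grip strength, countermovement jump, average exit speed". The same sentence goes on to list maximum exit speed, average and maximum fastball speed, and spin rate, so it covers all seven outcomes. No period or sequence term appears anywhere in the Protocol.

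**The concern.** A paired t-test treats each player's caffeine-minus-placebo difference as the caffeine effect plus noise. In a two-period crossover that difference also contains the change from week 1 to week 2, with a plus sign for players who had placebo first and a minus sign for those who had caffeine first. Learning, training, fatigue or field conditions could all cause such a change.

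If the two sequences differ in size, the signs do not cancel and part of the week effect is reported as a caffeine effect, in either direction. If they are equal in size, the signs cancel in the mean but still widen the spread of the differences, so the test loses power. With only 10 and 14 players, both matter. The test is named in the Protocol, so this is a stated choice and not a detail left to a statistical analysis plan.

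**Working it through.** **Inputs from the Protocol.** n = 10 pitchers and n = 14 fielders (Project summary, Participants); two periods one week apart; significance level 0.05, taken here as two-sided. The Protocol states no power, bias or sample-size figure, so there is none to reproduce.

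**Assumptions, not in the Protocol.** The SD of the within-player difference is set to 1. The week-2 minus week-1 shift π is 0, 0.25, 0.5 or 1.0 of that SD. Errors are normal.

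**Model.** Let d be caffeine minus placebo for one player, with a players placebo-first, b caffeine-first and n = a + b. Then d = τ + π + e for placebo-first and d = τ − π + e for caffeine-first.

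**Step 1: bias of the paired estimate.** E(mean d) = τ + π(a − b)/n.
- Pitchers 7/3, π = 0.5: 0.5 × 4/10 = 0.20 SD.
- Pitchers 8/2, π = 0.5: 0.5 × 6/10 = 0.30 SD.
- Fielders 9/5, π = 0.5: 0.5 × 4/14 = 0.14 SD.
- Any equal split: 0.

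**Step 2: inflation of the error term.** The expected variance of d used by the paired test is 1 + 4π²ab/[n(n − 1)]. For pitchers 5/5:
- π = 0.5: 1 + 4 × 0.25 × 25/90 = 1.28, an SD of 1.13.
- π = 1.0: 1 + 4 × 25/90 = 2.11, an SD of 1.45.

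**Step 3: operating characteristics.** These come from simulation, with at least 150,000 trials per setting. The comparator is the period-adjusted t-test, which averages the two sequence means of d with n − 2 degrees of freedom. Its standard error is ½√(1/a + 1/b).

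| Split | Bias (SD) at π = 0.25 / 0.5 / 1.0 | Paired type I error at the same π |
|---|---|---|
| Pitchers 5/5 | 0 / 0 / 0 | 4.4 / 3.0 / 0.7% |
| Pitchers 6/4 | 0.05 / 0.10 / 0.20 | 4.7 / 3.7 / 1.7% |
| Pitchers 7/3 | 0.10 / 0.20 / 0.40 | 5.4 / 6.0 / 6.3% |
| Pitchers 8/2 | 0.15 / 0.30 / 0.60 | 6.6 / 10.6 / 20% |
| Fielders 7/7 | 0 / 0 / 0 | 4.4 / 3.0 / 0.6% |
| Fielders 8/6 | 0.04 / 0.07 / 0.14 | 4.5 / 3.6 / 1.3% |
| Fielders 9/5 | 0.07 / 0.14 / 0.29 | 5.1 / 5.2 / 4.3% |
| Fielders 10/4 | 0.11 / 0.21 / 0.43 | 6.1 / 8.3 / 12% |

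The adjusted test stays at 5% in every setting.

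Power for pitchers with a true effect of 1.0 SD:
- 5/5: paired 80, 78, 72 and 48% for π = 0, 0.25, 0.5 and 1.0; adjusted 79% throughout.
- 7/3 at π = 0.5: paired 88% if seven are placebo-first, 53% if seven are caffeine-first; adjusted 72% in both.

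**Step 4: how likely are uneven splits?** Under simple randomisation an exactly equal split has probability 24.6% (n = 10) and 20.9% (n = 14). Among pitchers, 7/3 or worse has probability 34%, and 8/2 or worse 11%. If only the overall total is held at 12/12, these are 21% and 4%.

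**The case against.** The strongest reply is that no harm is shown. The Protocol gives no sign of a shift, and several controls work against one: familiarisation ("At least two familiarization tests were conducted one week before the formal trial"), the 72-hour limit on hard exercise, the repeated diet, the same clock time and the standardised warm-up. The players have at least six years of training, and the averages are taken over up to 30 pitches or 25 swings. A shift of 1.0 SD is therefore an extreme assumption. Averaged over simple randomisation, the bias is zero and the paired test's type I error is 5.0–5.2%. Clear inflation needs about 8/2 or 10/4 together with a sizeable shift.

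The paired test is also the better one on average when the shift is small. For pitchers under simple randomisation and an effect of 1.0 SD, its power against the adjusted test is 80% v 74% at π = 0, 78% v 74% at 0.25 and 71% v 74% at 0.5. Even at a fixed 7/3 split with π = 0.25, its root mean squared error is lower: √(1/10 + 0.10²) = 0.33 against ½√(1/7 + 1/3) = 0.345. At π = 0.5 the order reverses: √(1/10 + 0.20²) = 0.37 against 0.345.

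All of this stands, and it limits the weight of the point. It does not remove it. The controls reduce a shift but cannot exclude one. The average over randomisation also does not describe the one split that occurred, on which the reported estimate rests. The planned analysis neither estimates the shift nor removes it.

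**Conclusion.** The concern holds as a conditional one. If a week-to-week shift exists, the planned estimate is biased for an unequal realised split and the planned test is conservative for an equal one. At shifts of 0.25 to 0.5 SD, the bias among pitchers is 0.10 to 0.20 SD at 7/3, and power at 5/5 (effect 1.0 SD) falls from 80% to 78–72%.

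Type I error is a lesser issue: it stays at or below about 6% except at the most uneven splits. The actual size cannot be fixed from the Protocol, because neither the shift nor the sequence counts are given; all values of π here are assumptions. The form of the flaw is certain and its practical size is not, so it merits correction without being a fatal defect.

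**What to change.** For each outcome, replace the paired t-test with the standard 2×2 crossover analysis: treatment, period and sequence as fixed effects and player as random. Equivalently, compare the week-2 minus week-1 differences between the two sequences with a two-sample t-test; half the placebo-first minus caffeine-first difference is the caffeine effect. Report that effect with its 95% confidence interval, and the number in each sequence for pitchers and for fielders.

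Balancing the sequences within pitchers and within fielders would help only if allocation were still open. The Protocol already reports how many players identified their gum ("4 of 14 (29%) fielders and 4 of 10 (40%) pitchers correctly determined the type of gum intervention"), so it appears complete.

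**Cost.** A small change of model, available in SPSS, and no new data. With equal sequences about one point of power is lost: the effect detectable with 80% power goes from 1.00 to 1.01 SD at n = 10 and from 0.81 to 0.82 SD at n = 14. With unequal sequences the price is higher:
- n = 10, effect 1.0 SD: adjusted power is 77% at 6/4, 72% at 7/3 and 60% at 8/2.
- n = 14, effect 0.81 SD: 79% at 8/6, 76% at 9/5 and 71% at 10/4.

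If there is no shift, the paired test would have about 80% power in each of these cases, and the difference is given up for nothing.
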